### **8.11.2 Study and Site Discontinuation**

The Sponsor has the right to terminate this study at any time. Reasons for terminating the study may include, but are not limited to, the following:

- The incidence or severity of adverse events indicates a potential health hazard to patients.
- Patient enrolment is unsatisfactory.

The Sponsor will notify the Investigator and Health Authorities if the study is placed on hold, or if the Sponsor decides to discontinue the study or development program.

The Sponsor has the right to replace an investigational site at any time. Reasons for replacing a site may include, but are not limited to, the following:

- Excessively slow recruitment
- Poor protocol adherence
- Inaccurate or incomplete data recording
- Non-compliance with the ICH guideline for GCP

## **9. ASSESSMENT OF SAFETY**

### **9.1 SAFETY PARAMETERS AND DEFINITIONS**

Safety assessments will consist of monitoring and recording adverse events, including serious adverse events and non-serious adverse events of special interest, measurement of protocol-specified safety laboratory assessments, measurement of protocol-specified vital signs, ECGs, and any other protocol-specified tests that are deemed critical to the safety evaluation of the study.

Certain types of events require immediate reporting to the Sponsor, as outlined in Section [9.4](#).

#### **9.1.1 Adverse Events**

According to the ICH guideline for GCP, an adverse event is any untoward medical occurrence in a clinical investigation patient administered a pharmaceutical product, regardless of causal attribution. An adverse event can therefore be any of the following:

- Any unfavourable and unintended sign (including an abnormal laboratory finding), symptom, or disease temporally associated with the use of a medicinal product, whether or not considered related to the medicinal product.
- Any new disease or exacerbation of an existing disease (a worsening in the character, frequency, or severity of a known condition), except as described in Section [9.3.5.10](#).
- Recurrence of an intermittent medical condition (e.g., headache) not present at baseline.
- Any deterioration in a laboratory value or other clinical test (e.g., ECG) that is associated with symptoms or leads to a change in study treatment or concomitant treatment or discontinuation from study drug.
- Adverse events that are related to a protocol-mandated intervention, including those that occur prior to assignment of study treatment (e.g., invasive screening procedures such as biopsies).

#### **9.1.2 Serious Adverse Events**

A serious adverse event is any adverse event that meets any of the following criteria:

- Fatal (i.e., the adverse event actually causes or leads to death).
- Life-threatening (i.e., the adverse event, in the view of the Investigator, places the patient at immediate risk of death).
- Requires or prolongs inpatient hospitalisation (see Section [9.3.5.10](#)).

- Results in persistent or significant disability/incapacity (i.e., the adverse event results in substantial disruption of the patient's ability to conduct normal life functions).
- Congenital anomaly/birth defect in a neonate/infant born to a mother exposed to study drug or to a mother whose partner was exposed to study drug.
- Significant medical event in the Investigator's judgment (e.g., may jeopardise the patient or may require medical/surgical intervention to prevent one of the outcomes listed above).

The terms "severe" and "serious" are not synonymous. Severity refers to the intensity of an adverse event (rated as mild, moderate, or severe, or according to a pre-defined grading criteria (e.g., NCI CTCAE v4.03 criteria; see Section 9.3.3); the event itself may be of relatively minor medical significance (such as severe headache without any further findings).

Severity and seriousness need to be independently assessed for each adverse event recorded on the eCRF.

Pregnancy of a female patient or of the female partner of a male patient is not reported as a serious adverse event and are reported on a specific Clinical Trial Pregnancy Reporting Form immediately, within 24 hours to the Sponsor (see description in Section 9.4.3).

Serious adverse events are required to be reported by the Investigator to the Sponsor immediately (i.e., no more than 24 hours after becoming aware of the event; see Section 9.4.2 for reporting instructions).

### **9.1.3 Non-Serious Adverse Events of Special Interest**

Not applicable in Part A. Based on the results from Part A, non-serious adverse events of special interest [AESI]) might be defined for Part B of the study. These AESIs are required to be reported by the Investigator to the Sponsor immediately (i.e., no more than 24 hours after becoming aware of the event; see Section 9.4 for reporting instructions).

## **9.2 SAFETY PLAN**

### **9.2.1 Safety Precautions**

Safety will be assessed by close monitoring and timely assessment of adverse events, serious adverse events, DLTs, laboratory parameters, robust cardiovascular assessments (blood pressure, heart rate, ECG, periodical Holter ECG monitoring, ECHO or MUGA, cardiac markers), the patient's medical condition (physical examination), and general well-being and activities of daily life (ECOG performance status). The CTCAE v4.03 will be used.

**Safety will be evaluated by:**

- Adverse events (according to CTCAE v4.03), AESIs in Part B if applicable, serious adverse events and adverse events leading to discontinuation or death
- The results of safety laboratory test, physical examination, vital signs, 12-lead ECGs, Holter Monitoring, LVEF and ECOG performance status
- Drug exposure, including dose intensities and dose modifications

**9.2.2 Dose-Limiting Toxicity (DLT)**

Refer to Section [7.4.4](#).

**9.2.3 Cardiac Monitoring**

Cardiovascular assessments will be performed as outlined in the Schedule of Assessments ([Appendix 1](#) and [Appendix 2](#)), and as detailed in Section [8.2.3](#).

**9.2.4 Criteria for Withdrawal from the Study**

Patients will be withdrawn from the study if the following criteria are met:

- Unequivocal disease progression
- Death
- Intervening illness that prevents further administration of treatment
- Unacceptable adverse events
- Intercurrent cardiac disease, especially drop in LVEF < 40% or drop > 15% from baseline (if LVEF with > 15% drop is still > 55% a second measurement after 1 week would be allowed before discontinuing the patient)
- Intercurrent interstitial lung disease or pneumonitis
- Patient non-compliance
- Pregnancy
- The patient decides to withdraw from study or is lost to follow-up
- General or specific changes in the patient's condition that render the patient not eligible for further treatment in the judgment of the Investigator
- If a patient experiences a DLT
- If a patient requires a continuous dose delay of more than 14 days (Part A and Part B) from the intended day of the next scheduled dose of CB-103
- If a patient is non-compliant and misses or forgets more than 3 sequential dosings on more than 1 occasion

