ion channel at high doses with a high peak concentration, suggest that CB-103 may have some potential to affect cardiac repolarisation and cardiac conduction. The clinical consequence of this finding is currently unknown as the translatability of ECG changes from dogs to humans is not known. As part of risk management, a robust, multiple ECG monitoring aligned with PK sampling - including periodical Holter monitoring, with concentration-response analysis and a central review performed by a cardiac expert - will be implemented in the study. Furthermore ECHO/MUGA scans will be performed at selected time points in the study to also investigate any effect of CB-103 on heart contractility. Patients should be monitored for clinical signs of heart abnormalities, and consideration be given to withdrawal from the study of any patients who develop signs of cardiac abnormalities taking into consideration overall benefit and risks for the patients.

Based on pre-clinical data with CB-103 and on information known from other drugs inhibiting the NOTCH pathway the following events might appear after CB-103 oral administration (see also Investigator's Brochure):

- ECG alterations
- Hypertensive events
- Cardiac dysfunction (New York Heart Association [NYHA] Class II-IV) including congestive heart failure with signs and symptoms of cardiac dysfunction such as dyspnoea, orthopnoea, increased cough, pulmonary oedema, S3 gallop, or reduced ventricular ejection fraction, that can be associated with fatal outcome.
- Increased extramedullary haematopoiesis (e.g. erythropoiesis)
- Splenomegaly
- Gastro-intestinal toxicities (diarrhoea, nausea, vomiting, abdominal pain)
- Mydriasis (dilated pupils)
- Phototoxicity
- Skin rash and redness
- Decreased physical activity and fatigue
- Decreased body weight
- Convulsions
- Oedema

The severity and seriousness of adverse events cannot be defined yet as this will be the first clinical study with CB-103. With respect to additional unknown risks, as per normal practice for Phase I, FIH clinical trials, the patients will be closely monitored in order to detect any additional, study drug-related adverse events.

The phototoxicity was deemed a hypothetical risk solely based on the UV spectrum peak absorption of the drug substance (CB-103 HCl) in the wavelength of 290 - 700 nm; phototoxicity was not observed in any pre-clinical studies with CB-103.

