### 2. Exclusionary concurrent medical conditions

- a. Impaired cardiac function or clinically significant cardiac diseases, including any one of the following:
1. Clinically significant cardiac disease including congestive heart failure (NYHA class III or IV), arrhythmia or conduction abnormality requiring medication, or cardiomyopathy
  2. Clinically uncontrolled hypertension (systolic blood pressure  $\geq 160$  mmHg or diastolic blood pressure  $\geq 100$  mmHg)

3. Complete left bundle branch block
  4. Right bundle branch block + left anterior hemiblock
  5. Mandatory use of a cardiac pacemaker
  6. Congenital long QT syndrome
  7. History or presence of sustained or symptomatic ventricular tachyarrhythmia
  8. Presence of atrial fibrillation
  9. Clinically significant resting bradycardia (< 50 bpm)
  10. Corrected QTcF > 450 ms for males and > 470 ms for females at the screening ECG
  11. QRS  $\geq$  110 ms
  12. History of symptomatic congestive heart failure
  13. Left ventricular ejection fraction (LVEF) < 50%. History of absolute decrease in LVEF of  $\geq$  15 absolute percentage points, or  $\geq$  10 absolute percentage points and crossing from > lower limits of normal (LLN) to < LLN on prior anti-cancer therapy (e.g. anti-HER2 therapy, anthracyclines), even if asymptomatic
  14. Angina pectoris  $\leq$  6 months prior to starting study drug
  15. Acute myocardial infarction (MI)  $\leq$  6 months prior to starting study drug
- b. General conditions or other clinically significant diseases, including any one of the following:
1. Haemorrhagic, embolic, or thrombotic stroke within 6 months prior to the first planned CB-103 treatment
  2. For patients with solid tumours: prior bone marrow/haematopoietic stem cell transplant.  
**Note:** For T-ALL patients prior allogenic bone marrow/haematopoietic stem cell transplant is allowed if they have no current GvHD and patients are off immunosuppressive therapy.
  3. Known infection with human immunodeficiency virus (HIV); or hepatitis B or C requiring treatment
  4. Any active infection requiring the use of parenteral anti-microbial agents or that is > Grade 2
  5. Non-malignant interstitial lung disease or pneumonitis
  6. Dyspnoea of any cause requiring supplemental oxygen therapy and dyspnoea at rest due to complications of advanced malignancy and co-morbidities

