#### 7.4.6.1.5 Cardiac Toxicities

As in non-clinical studies with CB-103, QT prolongation was observed at higher doses and ECG changes in patients may be observed, therefore, intensive cardiac monitoring is implemented into this study with central management and review of multiple ECGs and Holter ECGs at selected timepoints. Furthermore ECHO/MUGA scans and cardiac markers will be assessed at selected time points. For toxicities related to QTc prolongation, refer to [Table 8](#) below. For all other cardiac toxicities, please follow the non-laboratory recommendations seen in Section [7.4.6.1.7](#).

**Table 8** Dose modifications for cardiac toxicities

Dose Modifications for CB-103	
Worst Toxicity CTCAE Grade unless otherwise specified (Value)	At any time during a cycle of CB-103 (including intended day of dosing)
Cardiac - Prolonged QTcF interval	
During Cycle 1:	
Absolute QTcF < 480 ms	Maintain dose level and ECG monitoring as per visit schedule.

Dose Modifications for CB-103	
Worst Toxicity CTCAE Grade unless otherwise specified (Value)	At any time during a cycle of CB-103 (including intended day of dosing)
Cardiac - Prolonged QTcF interval	
QTcF $\geq$ 480 ms and $<$ 500 ms	Maintain dose level. ECG monitoring assessments should be increased as indicated (e.g. hourly until no QTcF $\geq$ 480 ms).
During any Cycle:	

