### 7.4.6.1.7 Non-Laboratory Toxicities

Patients who experience non-laboratory toxicities related to CB-103 must be evaluated at least once a week following demonstration of the toxicity until resolution of the toxicity to allow for re-treatment, stabilisation of the toxicity, or study treatment completion.

**Table 10** Dose modifications for non-laboratory toxicities

Dose Modifications for CB-103 post cycle 1	
Worst Toxicity CTCAE Grade  unless otherwise specified (Value)	At any time during a cycle of CB-103 (including intended day of dosing)
Non-laboratory adverse events	
Grade 1 or 2	Maintain dose level
Grade 3	Omit dose administration until resolved to $\leq$ grade 1, then $\downarrow$ 1 dose level
Grade 4	Omit dose administration and discontinue patient from study

 Common Terminology Criteria for Adverse Events (CTCAE Version 4.03)

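### Protocol 9.2.4 and Table 10 give different instructions for a CB-103-related Grade 1-3 fall in LVEF after cycle 1, and the 15% LVEF limit has no stated scale

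*Protocol*

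**What the plan says.** Protocol 9.2.4 opens with mandatory force: "Patients will be withdrawn from the study if the following criteria are met". Its cardiac item reads "Intercurrent cardiac disease, especially drop in LVEF < 40% or drop > 15% from baseline". The one relief is a repeat: if LVEF after a drop above 15% "is still > 55% a second measurement after 1 week would be allowed before discontinuing the patient". The item carries no CTCAE grade and no causality condition.

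Protocol 7.4.6.1.5 deals with QTc prolongation in Table 8 and then says "For all other cardiac toxicities, please follow the non-laboratory recommendations seen in Section" 7.4.6.1.7, that is, Table 10. That table keeps the dose at Grade 1 or 2. At Grade 3 it holds dosing until the event is Grade 1 or lower and then drops one dose level. At Grade 4 it says "Omit dose administration and discontinue patient from study". Its header confines it to the time after cycle 1, and 7.4.6.1.7 covers toxicities related to CB-103. Section 7.4.6.1 makes these tables instructions to the investigator.

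Protocol 3.2 says that ECHO/MUGA scans will be done "to also investigate any effect of CB-103 on heart contractility", and then asks that "consideration be given to withdrawal from the study of any patients who develop signs of cardiac abnormalities", in the light of overall benefit and risk.

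Exclusion criterion 2a.13 excludes LVEF below 50%. It states its unit for past falls in LVEF explicitly, for example "absolute percentage points and crossing from > lower limits of normal (LLN) to < LLN on prior anti-cancer therapy". Section 9.2.4 states no unit for its 15%.

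**The concern.** Two operative sections govern the same patient and point different ways. One removes the patient from the study at a numerical LVEF limit. The other lets treatment continue, at the same or a lower dose, unless the event reaches Grade 4. I found no sentence that says which prevails. A second gap sits inside the withdrawal rule itself: a fall of more than 15% can be measured against the baseline value or in LVEF points, and the two give different cut-offs.

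Reduced ejection fraction is among the potential risks listed in 3.2, and ECHO/MUGA is part of the confirmatory cohort's primary endpoint (4.2.1). In a multi-centre study, two sites that each follow the protocol could treat the same patient differently. That bears on patient safety and on the count of withdrawals for cardiac reasons.

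**Working it through.** The plan states no figure to reproduce. The check is a comparison of passages, then arithmetic on the two readings of the 15%.

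**Step 1: the two rules side by side.** Take a CB-103-related event after cycle 1 in which LVEF has crossed a 9.2.4 limit.

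| CTCAE grade | 9.2.4 | 7.4.6.1.5 and Table 10 | Agree? |
|---|---|---|---|
| 1-2 | withdraw | keep dose | no |
| 3 | withdraw | hold, then one level down | no |
| 4 | withdraw | discontinue from study | yes |

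The on-treatment ECHO/MUGA scans are at Cycle 1 Day 8, Cycle 3 Day 1 and end of treatment (8.2.3.3), with extra scans at the investigator's discretion. At Cycle 1 Day 8 the Table 10 header takes the event out of that table. A cardiac event of Grade 3 or above that meets the DLT definition is then a DLT, and a DLT is itself a 9.2.4 withdrawal criterion. The scheduled scan at which the clash arises during treatment is therefore Cycle 3 Day 1. For illustration, assume an LVEF of 38% there, judged related and graded 3: 9.2.4 withdraws the patient, while Table 10 allows a return at a lower dose.

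**Step 2: the scale of the 15%.** Inputs: limits of 40% and 15% (9.2.4), and a baseline b of at least 50% (exclusion criterion 2a.13). I read the first limit as LVEF below 40%.

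- Absolute cut = b - 15
- Relative cut = 0.85 × b
- Trigger = the larger of 40 and the cut

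| Baseline LVEF (%) | Absolute cut | Relative cut | Trigger, absolute | Trigger, relative | Difference (points) |
|---|---|---|---|---|---|
| 50 | 35 | 42.5 | 40 | 42.5 | 2.5 |
| 55 | 40 | 46.75 | 40 | 46.75 | 6.75 |
| 60 | 45 | 51 | 45 | 51 | 6 |
| 65 | 50 | 55.25 | 50 | 55.25 | 5.25 |
| 70 | 55 | 59.5 | 55 | 59.5 | 4.5 |
| 75 | 60 | 63.75 | 60 | 63.75 | 3.75 |

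Example: a fall from 60% to 50% is 10/60 = 16.7% on the relative reading, which meets the limit. It is 10 points on the absolute reading, which does not.

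The scale also decides whether the 15% limit adds anything to the 40% limit. On the absolute reading it does so only if b - 15 > 40, so b > 55. On the relative reading it does so if 0.85b > 40, so b > 47.1, which covers every eligible patient.

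**Step 3: the repeat-measurement clause.** It can apply if the trigger lies above 55: b - 15 > 55 gives b > 70 (absolute), and 0.85b > 55 gives b > 64.7 (relative). It is workable on either reading, so it does not reveal which was meant.

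It does change what the table means at high baselines:

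- **Baseline 65%:** withdrawal without a repeat applies at 55% or lower (relative) against below 50% (absolute), still 5 points apart.
- **Baseline 70%:** on the relative reading, values above 55% and below 59.5% lead to a permitted repeat. Withdrawal without a repeat applies at 55% or lower (relative) against below 55% (absolute), which is almost the same.
- **Baseline 75%:** withdrawal without a repeat applies at 55% or lower on both readings. They differ only in whether a value from 60% to just under 63.75% triggers a repeat.

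**The case against.** The best defence is that the sections do different jobs. Table 10 is general dose-modification guidance and 9.2.4 is a specific list of withdrawal criteria, so a careful reader would let the specific list override. That is reasonable but not written down, and the protocol does not let a site rely on it. Table 8 classes a QTcF of 500 ms or more as a DLT and still allows re-treatment one level lower, while 9.2.4 withdraws any patient with a DLT.

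It can also be said that 9.2.4 concerns intercurrent disease, which the DLT definition treats as an alternative to drug toxicity, so the two passages cover different events. The LVEF limits themselves, however, carry no causality condition.

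Several stronger readings are tempting, and the documents do not support them:

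- **Section 3.2 as a third conflicting rule.** It is risk-benefit background on any sign of cardiac abnormality. Considering withdrawal for any sign is compatible with requiring it at stated limits. It needs aligning, no more.
- **A conflict at every grade, in every cycle and whatever the cause.** Table 10 agrees with 9.2.4 at Grade 4 and is confined to related events after cycle 1.
- **Criterion 2a.13 as settling the scale.** It concerns past falls on earlier anti-cancer therapy. It shows that a unit can be stated, not which unit 9.2.4 intends.
- **Damage to the confirmatory endpoint, exposure or response data.** ECHO/MUGA results are recorded whichever rule is followed, and the documents give no rate of LVEF falls from which to size an effect.

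**Conclusion.** The point stands in two parts. First, for a CB-103-related Grade 1-3 fall in LVEF after cycle 1 that crosses a 9.2.4 limit, 9.2.4 and Table 10 contradict each other with no stated precedence. Second, the 15% limit has no scale. At the tabulated baselines from 50% to 65% the two readings move the trigger by 2.5 to 6.75 LVEF points; at about 70% and above they differ mainly in whether a repeat measurement is called for. The second part applies in cycle 1 as well and does not depend on Table 10.

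The conclusion assumes that an LVEF fall counts as one of the other cardiac toxicities in 7.4.6.1.5. The documents give no CTCAE grading of LVEF falls, so the Table 10 row for a given patient cannot be derived from them; any grade from 1 to 3 produces the conflict. The SAP does not resolve either part: its section 5.7.4 summarises LVEF only in normal and abnormal categories. This is a wording defect with a safety consequence and should be corrected.

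**What to change.** Reconcile 9.2.4 with 7.4.6.1.5 and Table 10 for LVEF decrease and new cardiac disease. Put the rule in one place, have the other passages refer to it, and state which takes precedence. Align the wording of 3.2 with it. State in 9.2.4, as explicitly as criterion 2a.13 does for its own limits, whether the 15% is relative to baseline or in percentage points. Then check that the 55% repeat clause works as intended on the chosen scale. Which rule and which scale apply is a decision for the sponsor and its cardiac experts; this review does not propose one.

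The cost is wording in three protocol sections and a note to sites. No assessments are added, since ECHO/MUGA is already scheduled.

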## 9.3 METHODS AND TIMING FOR CAPTURING AND ASSESSING SAFETY PARAMETERS

The Investigator is responsible for ensuring that all adverse events (see Section 9.1.1 for definition) are recorded on the Adverse Event eCRF and reported to the Sponsor in accordance with instructions provided in this section and in Sections 9.4 to 9.5.

For each adverse event recorded on the Adverse Event eCRF, the Investigator will make an assessment of seriousness (see Section 9.1.2 for seriousness criteria), severity (see Section 9.3.3), and causality (see Section 9.3.4).

Follow-up by the Investigator may be required until the event or its sequelae resolve or stabilise at a level acceptable to the Investigator, and Sponsor concurs with that assessment. As part of ongoing safety reviews conducted by the Sponsor, any non-serious adverse event that is determined by the Sponsor to be serious will be reported by the Sponsor as a serious adverse event. To assist in the determination of case seriousness further information may be requested from the Investigator to provide clarity and understanding of the event in the context of the clinical trial.

